## Efficacy Measures:

- IGA

Grade		Description
0	Clear	
 
• No comedones, papules or pustules
 
• Residual hyperpigmentation and erythema may be present
 

1	Almost Clear	
 
• Rare comedones
 
• No more than a few small papules and pustules
 

2	Mild	
 
• Easily recognizable comedones in limited numbers
 
• +/- Presence of small papules and pustules
 

3	Moderate	
 
• Many comedones
 
• +/- Easily recognizable small and medium-sized papules
 
• No nodules or cysts.
 

4	Severe	
 
• Widespread and numerous comedones
 
• Many small, medium-sized and large papules and pustules
 
• Nodules or cysts may or may not be present.
 

(Eichenfield et al, 2013, J of Dermatol)

- Local dermal tolerability assessment

The local tolerability examination of the face is to be performed by the investigator (or appropriately trained designee), who will assess dryness, scaling, and erythema, and the patient will assess stinging/burning. The assessor will examine the skin area where study drug is applied in comparison to the surrounding skin from day 1 to week 12. The same assessor will rate dryness, scaling, and erythema at each visit, where possible. Local tolerability signs and symptoms will be rated using a severity scoring of 0 (none), 1 (mild), 2 (moderate), or 3 (severe), as further defined below.

Based on the assessor's medical judgment, if a sign or symptom is clinically significant, it must be recorded on the adverse event eCRF. Other dermatological findings of clinical significance in the patient's treated area must also be reported as adverse events on the eCRF.

*Patient-rated:*Stinging/Burning: prickling pain sensation immediately after (within 5 minutes of dosing, except baseline)

None (0) = No stinging/burning

Mild (1) = Slight warm, tingling/stinging sensation; not really bothersome

Moderate (2) = Definite warm, tingling/stinging sensation that is somewhat bothersome

Severe (3) = Hot, tingling/stinging sensation that has caused definite discomfort

*Investigator- (or designee) rated:*Dryness: brittle and/or tight sensation

None (0) = No Dryness

Mild (1) = Slight but definite roughness

Moderate (2) = Moderate roughness

Severe (3) = Marked roughness

Scaling: abnormal shedding of the stratum corneum

None (0) = No Scaling

Mild (1) = Barely perceptible shedding, noticeable only on light scratching or rubbing

Moderate (2) = Obvious but not profuse shedding

Severe (3) = Heavy scale production

Erythema: abnormal redness of the skin

None (0) = No Erythema

Mild (1) = Slight pinkness present

Moderate (2) = Definite redness, easily recognized

Severe (3) = Intense redness

- Fitzpatrick skin phototype (FDA Federal Register, 1999):
  - I: Always burns easily; never tans (sensitive)
  - II: Always burns easily; tans minimally (sensitive)
  - III: Burns moderately; tans gradually (light brown) (normal)
  - IV: Burns minimally; always tans well (moderate brown) (normal)
  - V: Rarely burns; tans profusely (dark brown) (insensitive)
  - VI: Never burns; deeply pigmented (insensitive)
  
- Photographs will be taken by a subset of study sites. Photographs will be transferred to the Sponsor on a periodic basis.

## 12.2 Handling of Biological Specimens

Details relating to the handling of biological samples are provided in the Procedure Manual.

## 12.3 Glossary of Abbreviations

Term/Abbreviation	Definition
CRF	case report form
C max	maximum plasma concentration
DHA	dapsone hydroxylamine
eCRF	electronic case report form
FDA	Food and Drug Administration
GCP	Good Clinical Practices
G6PD	glucose-6-phosphate dehydrogenase
HIPAA	Health Insurance Portability and Accountability Act
ICH	International Conference on Harmonisation
IEC	Independent Ethics Committee
IETD	investigator emergency treatment disclosure
IRB	Institutional Review Board
IVRS	interactive voice response system
IWRS	interactive web response system
MedDRA	Medical Dictionary for Regulatory Activities
mITT	modified intent-to-treat
NAD	N-acetyl dapsone
NSAID	nonsteroidal anti-inflammatory drug
PK	Pharmacokinetics
PT	preferred term
SOC	system organ class
TEAE	treatment-emergent adverse event
US	United States

2.2 List of Figures

Not applicable.

3. List of Abbreviations and Definition of Terms

Table 3-1 Abbreviations and Definitions of Terms

Abbreviation/Term	Definition
AE	adverse event
ATC	Anatomical Therapeutic Chemical
CFB	change from baseline
DHA	dapsone hydroxylamine
eCRF	electronic case report form
IGA	Investigator's Global Assessment
MedDRA	Medication Dictionary for Regulatory Activities
mITT	modified intent-to-treat
NAD	N-acetyl dapsone
PK	pharmacokinetic
PT	preferred term
SAE	serious adverse event
SAP	statistical analysis plan
SI	Le Système International d'Unités (International System of Units)
SOC	system organ class
TEAE	treatment-emergent adverse event

4. Introduction

This statistical analysis plan (SAP) details comprehensive, technical specifications of the statistical analyses of the efficacy and safety data outlined and/or specified in the final protocol of Study 1679-401-006 dated 23-Jun-2016. Specifications of tables, figures, and data listings are contained in a separate document. The SAP for pharmacokinetic (PK) data will be prepared separately.

This document is organized into 3 main sections:

- 1. Study Overview
- 2. Statistical Methodology and Study Endpoints
- 3. Data Handling and Analysis Conventions

4.1 Study Design Summary

Structure: Multicenter, open-label, non-comparative trial

Duration: Patient participation is up to approximately 16 weeks from screening to trial exit;

treatment duration is up to 12 weeks

Study Treatment Groups: ACZONE 7.5%

Controls: No control group

Dosage/Dose Regimen: All patients will receive treatment with ACZONE 7.5% once-daily Pharmacokinetic (PK) Cohort (at least 16 evaluable PK patients): For the first 8 days (+ 2 days), study drug will be administered once-daily under maximal use condition (~2 grams/day) to the entire face, neck, upper chest, upper back and shoulders as instructed by the study site. The study drug should be rubbed in gently and completely. On Day 1, the study drug will be administered on site. From Day 2 through Day 7, the study drug will be administered in the morning at home by the patient's legally authorized representative. At the Week 1/Visit 3 [Day 8 (+2 days)], the study drug will be administered on site in the morning. After the Week 1/Visit 3, patients or the patient's legally authorized representative will apply a pea-sized amount of study drug in a thin layer to the patient's face, once-daily, at home for the remaining 11 weeks, the same as the dose regimen for the Non-PK Cohort. Acne-affected areas on the upper chest, upper back, and shoulders should also be treated with a thin layer during the final 11 weeks. Evaluable PK patients are defined as those that are administered at least 8 days of study drug under maximal use conditions, and provided PK samples for analysis without any major protocol deviations.

Non-PK Cohort (approximately 84 patients): Patients or the patient's legally authorized representative will apply a pea-sized amount of study drug in a thin layer to the patient's face

once-daily for 12 weeks as instructed by the study site. Acne-affected areas on the upper chest, upper back, and shoulders should also be treated with a thin layer.

Randomization/Stratification: No randomization; all patients will receive ACZONE 7.5%. Assignment to PK or Non-PK Cohort will be based on patient/legally authorized representative choice and investigator's judgment.

Visit Schedule: up to 7 scheduled study visits (see Table 4-2 for further details):

- Visit 1: Screening (-30 to day -1)
- Visit 2: Day 1 (Baseline)^a
- Visit 3: Week 1 (Day 8 + 2 days)
- Visit 4: Week 2 (±3 days)
- Visits 5 and 6: Weeks 4 and 8 (\pm 7 days)
- Visit 7: Week 12 / Early Exit (±7 days)

Number of Participants: For the PK Cohort, at least 16 patients will be enrolled to ensure 16 evaluable PK subjects at the Week 1 visit. For the Non-PK Cohort, approximately 84 additional patients will be enrolled in the study for a total of approximately 100 patients.

4.2 Study Objectives and Endpoints

Each study objective is presented with corresponding endpoint(s) below:

Table 4-1 Study Objectives and Corresponding Endpoints

Objectives	Endpoints
To evaluate the safety and tolerability of ACZONE 7.5% administered topically oncedaily for 12 weeks in 9 to 11 year-olds with acne vulgaris.	Safety Assessments Adverse events (AE) Vital signs Heart rate Blood pressure Respiratory rate Body temperature Local dermal tolerability (face only) Dryness Scaling Erythema Stinging/burning
To evaluate the peak and trough plasma drug concentrations in 9 to 11 year-olds with acne vulgaris following once-daily dosing of	Peak and trough plasma concentrations of dapsone, N-acetyl dapsone (NAD), dapsone hydroxylamine

^a Can be combined with the screening visit if no washout period is required.

Objectives	Endpoints			
ACZONE 7.5% under maximal use conditions for the first 8 days (+ 2 days).	(DHA), and other metabolites or analytes (if warranted) at Week 1/Visit 3			
To explore the efficacy of ACZONE 7.5%	Efficacy Assessments			
administered topically once-daily in 9 to 11	Lesion counts (face only)			
year-olds with acne vulgaris.	 Change and percent change from baseline in inflammatory lesion counts 			
	 Change and percent change from baseline in noninflammatory lesion counts 			
	 Change and percent change from baseline in total lesion counts (Total lesion counts will be the sum of inflammatory lesion counts and noninflammatory lesion counts.) 			
	• Investigator's Global Assessment (IGA) (face only)			
	 Proportion of patients with none (0) or minimal (1) score on the IGA at each visit 			
	 Proportion of patients with none (0) or 			
	minimal (1) score plus at least a 2-grade			
	improvement on the IGA at each visit			

4.3 Schedule of Activities

Table 4-2Schedule of Activities

Study Period	Screeninga	Baseline/Day 1 ^a	Week 1	Week 2	Weeks 4 and 8	Week 12/ Early Exit
Visit Number	Visit 1	Visit 2	Visit 3	Visit 4	Visit 5 and Visit 6	Visit 7
Visit Windows	Day -30 to Day -1	N/A	Day 8 (+ 2 days)	Day 15 (± 3 days)	Day 29 (± 7 days) and Day 57 (± 7 days)	Day 85 (± 7 days)
Informed consent/authorization and minor assent ^b	X					
Inclusion/exclusion criteria	X	X				
Medical/surgical history	X					
Demographics	X					
Skin phototype assessment	X					
Physical examination includes vital signs, height and weight ^c	X					X
Pregnancy test (urine) ^d	X	X			X	X
IGA	X	X	X	X	X	X
Lesion count	X	X	X	X	X	X
Enrollment		X				
PK Cohort: Dispense study drug, training on application/return ^e		D	R/D		R/D	R
Non-PK Cohort: Dispense study drug, training on application/return ^f		D			R/D	R
Standardized photographs ^g		X				X
Local tolerability ^h		X	X	X	X	X
Concomitant medications	X	X	X	X	X	X
Concomitant procedures	X	X	X	X	X	X

Study Period	Screening ^a	Baseline/Day 1 ^a	Week 1	Week 2	Weeks 4 and 8	Week 12/ Early Exit
Visit Number	Visit 1	Visit 2	Visit 3	Visit 4	Visit 5 and Visit 6	Visit 7
Visit Windows	Day -30 to Day -1	N/A	Day 8 (+ 2 days)	Day 15 (± 3 days)	Day 29 (± 7 days) and Day 57 (± 7 days)	Day 85 (± 7 days)
Adverse events	X	X	X	X	X	X
PK sampling ⁱ			X			

D = dispense; IGA = Investigator's Global Assessment; N/A = not applicable; R = return; PK= pharmacokinetic

- ^a If a washout period is not required, then screening and baseline visits can occur on the same day, and the procedures required to be repeated at both visits should be performed once.
- b Consent for photography is included in the informed consent process at select centers.
- Physical examination and vital signs are to be performed if inclusion/exclusion criteria are met at screening; not required for screen failures. Vital signs include heart rate, blood pressure, respiratory rate, and body temperature.
- Female patients only. The urine pregnancy test can also be performed at any timepoint during the course of the trial at the investigator's discretion. If a patient misses a menstrual cycle, a urine pregnancy test must be performed.
- Patients in the PK cohort will be dispensed 1 kit with 14 tubes on Baseline/Day 1 (Visit 2). All patients in the PK cohort will start dosing on Day 1 using the 2.0 gram tubes dispensed for individual application. PK Cohort patients will return used study drug at Week 1/Visit 3. At Week 1/Visit 3, Week 4 (Visit 5) and Week 8 (Visit 6) the patients in the PK Cohort are dispensed 60-gram pumps. Dispensed and returned study drug will be weighed at the study center.
- All patients will start dosing on day 1. The patients in the Non-PK Cohort are dispensed 60-gram pumps on Baseline/Day 1 (Visit 2), Week 4 (Visit 5) and Week 8 (Visit 6). Dispensed and returned study drug will be weighed at the study center.
- At select centers, patients may have photographs taken of their face for illustration or presentation purposes. Patients who consent to being photographed will be required to remove any make-up at least 20 minutes prior to having photographs taken.
- ^h Local tolerability will be assessed prior to drug administration on day 1, as well as postdose on the face only.
- Only applies to patients in the PK Cohort at the Week 1/Visit 3. Blood samples will be collected within 30 minutes prior to dosing in clinic in the morning and at approximately 10 hours post dose (± 3 hour) (patients are allowed to leave and come back if needed) under maximal use conditions to determine the peak and trough plasma drug concentrations.

5. Statistical Methodology and Study Endpoints

5.1 Statistical Methods Planned in the Protocol and Determination of Sample Size

This SAP will be approved prior to database lock. The SAP expands the statistical section of the protocol and contains a detailed description of methods to analyze data collected in the study. The text portion of the SAP will be included in the CSR report as Appendix 16.1.9. Information on the PK analyses can be found in the PK data analysis plan.

5.1.1 Statistical and Analytical Plans

Statistical analyses will be conducted using SAS Version 9.3 or newer.

5.1.1.1 Common Conventions

5.1.1.1.1 Analysis Populations

The analysis populations will consist of participants as defined below:

Table 5-1 Analysis Populations

Population	Definition	Study Treatment
Screened	All screened participants who sign informed consent.	_
Safety	All participants who received at least one application of study drug.	Actual received
Modified Intent-to- Treat (mITT)	All enrolled participants who have a baseline assessment and at least one post-baseline assessment.	Actual received

5.1.1.1.2 Study Treatments

The following treatment group is defined for this study:

• ACZONE 7.5%

5.1.1.1.3 Statistical Methodology

The methodologies defined below apply as specified to individual endpoints defined in this SAP.

Table 5-2 Statistical Methodology

Methodology	Description		
Categorical counts	Number of participants in individual categories		
	 ○ Participants with ≥ 1 qualifying event counted once per individual category 		
Categorical	Number and percentage of participants in individual categories		
descriptives	 ○ Participants with ≥ 1 qualifying event counted once per individual category 		
	• N1 if percentage denominator ≠ number of participants in the population (standard		
	percentage denominator)		
	 N1 = participants with non-missing baseline value 		

Methodology	Description			
Continuous	N1, mean, standard deviation (SD), median, minimum, maximum			
descriptives	• N1 = participants with non-missing value			
CFB ¹ descriptives	 Continuous descriptives for baseline, postbaseline, and change from baseline (CFB) values N1 = participants with non-missing values at both baseline and the specified postbaseline analysis visit 			

¹CFB = change from baseline

Raw and derived data listings will be provided, and will be fully defined in the table, figure, and data listing specification document.

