## **4. Study Population and Entry Criteria**

### **4.1 Number of Patients**

For the PK Cohort, at least 16 subjects will be enrolled to ensure 16 evaluable PK subjects at the Week 1 visit. For the Non-PK Cohort, approximately 84 additional patients will be enrolled in the study for a total of approximately 100 patients. PK Cohort patients who discontinue from the trial prior to either of the PK blood draws scheduled at Week 1/Visit 3

(or who otherwise do not have evaluable PK samples) will be replaced. Assuming an attrition rate of 15%, approximately 85 patients are expected to complete the 12-week trial.

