### 7.1 Analyses Populations

The following 3 analysis populations will be utilized:

1. The safety population includes all patients who are treated with at least one application of study drug.
2. The modified intent-to-treat (mITT) population includes all enrolled patients who have a baseline assessment and at least one post-baseline assessment.
3. The PK population will be defined as all patients who received applications of study drug for at least 8 days under maximal use conditions and have evaluable blood samples for PK analysis. This population will be used for PK analyses.

Safety analyses will be based on the safety population. Efficacy analyses will be based on the mITT population. No imputation for missing data will be performed for safety or efficacy analyses.

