### 7.3 Efficacy Analysis

All efficacy analyses are considered exploratory and will be performed using the mITT population. All efficacy summaries will use data from both study cohorts combined.

For lesion counts, change and percent change from baseline in inflammatory lesion counts will be summarized using descriptive statistics. Baseline is the predose measurement on Day 1. Inflammatory lesion counts include papules, pustules, nodules and cysts. The same summarizations will be done for noninflammatory lesion counts and total lesion counts. Noninflammatory lesion counts include open and closed comedones, and total lesion counts include inflammatory and noninflammatory lesion counts.

If a number of patients have fewer than 5 inflammatory or noninflammatory lesions at baseline, an additional analysis may be conducted for that lesion type including only those patients with at least 5 lesions of that type at baseline.

A frequency distribution will be used to summarize the proportion of patients with none (0) or minimal (1) score on the IGA at each visit. In addition, a frequency distribution will be used to summarize the proportion of patients with none (0) or minimal (1) score plus at least a 2-grade improvement on the IGA at each visit.

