5.1.1.1.4 Missing Data

No imputation of missing efficacy data for this study is specified for methodologies in Section 5.1.1.1.3.

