6.2.1 Efficacy

The analysis visit windows for efficacy endpoints are defined as follows:

Table 6-2 Efficacy Analysis Visit Definitions

Analysis Phase	Analysis Visit (Derived)	Target/Study Visit (eCRF)	Window
Pretreatment	Baseline	Day 1/Visit 2	Treatment Day ≤ 1 , pre-dose
Treatment	Week 1	Day 8/Visit 3	Treatment Day [6, 11]
	Week 2	Day 15/Visit 4	Treatment Day [12, 21]
	Week 4	Day 29/Visit 5	Treatment Day [22, 42]
	Week 8	Day 57/Visit 6	Treatment Day [43, 70]
	Week 12	Day 85/Visit 7	Treatment Day [71, last dose + 14
		•	days]

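### The Week 12 lesion-count change is an observed-case mean labelled mITT: it leaves out up to about 15% of that population at the planned attrition, and overstates the reduction if those who leave respond worse

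*SAP*

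**What the plan says.** Protocol 7.3 sets the population: "All efficacy analyses are considered exploratory and will be performed using the mITT population". SAP Table 5-1 defines mITT as enrolled participants with a baseline and at least one post-baseline assessment.

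SAP Table 5-10 summarises inflammatory, noninflammatory and total lesion counts by analysis visit with the change-from-baseline method. Table 5-2 gives that method's denominator: "N1 = participants with non-missing values at both baseline and the specified postbaseline analysis visit". SAP 5.1.1.1.4 adds "No imputation of missing efficacy data for this study is specified for methodologies in Section 5.1.1.1.3", and Protocol 7.1 agrees: "No imputation for missing data will be performed for safety or efficacy analyses".

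The IGA proportions use the categorical method. Its percentages are taken over the population or, where the denominator differs, over "N1 = participants with non-missing baseline value".

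Lesion counts are also taken at early exit (Protocol 6.2.2 and 8.4.5). Table 5-10 names its last timepoint as Week 12 or early exit, but Table 6-2 assigns visits by treatment day and gives Week 12 the window beginning "Treatment Day [71, last dose + 14" days.

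On expected loss, Protocol 4.1 says: "Assuming an attrition rate of 15%, approximately 85 patients are expected to complete the 12-week trial".

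**The concern.** At Week 12 the population named and the patients averaged are not the same. A child who leaves at Week 6 belongs to mITT, and has counts at Weeks 1, 2 and 4, but contributes nothing to the Week 12 mean. The row then answers how much the patients still being counted improved. That differs from how much the mITT patients improved whenever leaving is related to response.

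The trial has no control group, so the mean change from baseline is itself the lesion-count result, and no between-arm difference can cancel selective loss. Part of any apparent gain between Week 4 and Week 12 could come from a change in who is counted.

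The two efficacy endpoints also treat the same child differently at Week 12. A leaver drops out of the lesion-count mean but stays in the IGA denominator, and the SAP does not explain why.

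**Working it through.** **The plan's own figure.** Enrolment is 16 + 84 = 100, in line with "approximately 84 additional patients will be enrolled in the study for a total of approximately 100 patients". At 15% attrition, 100 × (1 − 0.15) = 85 completers, which reproduces the protocol's number.

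**Who enters the Week 12 row.** Under Table 6-2, an exit count before Day 71 falls in an earlier window. An exit on Day 35, for example, falls in the Week 4 window (Days 22 to 42). If that patient also has a Day 29 count, SAP 6.2 keeps the one closest to target, so the exit count enters no summary row. A patient who exits on or after Day 71 is counted at Week 12. The row is therefore close to completers, but not identical to them.

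**Share of mITT missing, m.** The 15% applies to enrolled patients. If x of the 15 leavers have no post-baseline assessment, they are not in mITT, and m = (15 − x)/(100 − x). This assumes that all 85 completers have a Week 12 count and that no leaver has one.

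- x = 0: 15/100 = 15.0%
- x = 3: 12/97 = 12.4%
- x = 5: 10/95 = 10.5%
- x = 10: 5/90 = 5.6%

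**Overstatement.** Let r be the leavers' mean change divided by the mean change of patients with a Week 12 count. The mITT mean is the observed mean × [(1 − m) + m·r], so the relative overstatement is 1/[(1 − m) + m·r] − 1. The documents give no r, so a range is shown, using m rounded as in the column heads.

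| r (assumed) | m = 15% | m = 10.5% | m = 5.6% |
|---|---|---|---|
| 1 | 0% | 0% | 0% |
| 0.75 | 3.9% | 2.7% | 1.4% |
| 0.5 | 8.1% | 5.5% | 2.9% |
| 0.25 | 12.7% | 8.5% | 4.4% |
| 0 | 17.6% | 11.7% | 5.9% |

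For example, at m = 15% and r = 0.5: 1/(0.85 + 0.075) − 1 = 1/0.925 − 1 = 8.1%. If patients with a count had a mean reduction of 50% (an assumption) and leavers 25%, the mITT mean would be 0.85 × 50 + 0.15 × 25 = 46.25%, which is 3.75 points lower. If r exceeds 1, the sign reverses.

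**IGA for comparison.** With 30 responders at Week 12 (an assumption), the proportion is 30/100 = 30% with leavers kept in the denominator, and 30/85 = 35.3% among those seen.

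**Would a repeated-measures mean help?** A simulation used 100 patients, five visits, a mean change of −20 lesions, SD 15 to 20, adjacent-visit correlation 0.7 to 0.85, and 15% dropout driven by the last observed response (all assumed; 1,500 replicates per setting). The observed-case mean was overstated by 3.6% to 7.4% under moderate dependence and 6.5% to 13.4% under strong dependence. On −20 lesions that is about 0.7 to 1.5 and 1.3 to 2.7 lesions. A likelihood-equivalent estimate was within 0.6% of the truth, with about the same standard error (1.5 to 2.2 lesions). With no dependence, both were unbiased.

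**The case against.** The strongest reply is that early-exit counts are collected and Table 5-10 names its last timepoint as Week 12 or early exit. If exit counts go into that row, most leavers are represented and much of the point falls away. A reader might infer that the gap exists under any visit-window rule, but it does not: it rests on Table 6-2. What stands is that the two tables are unreconciled. The alternative reading would mix, say, a Day 30 count with Day 85 counts, which is a carry-forward that the SAP does not state.

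A reader might also infer that the whole efficacy summary describes completers. That is not so, because the IGA denominators keep leavers in.

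A third tempting inference is that the reduction will be overstated. The documents link dropout to tolerability, voluntary withdrawal and unwillingness to comply (Protocol 5.4.2, 8.8, 8.9), and nowhere to lesion response. The simulation assumes response-driven dropout, so it shows how the estimators behave and is not evidence about this trial.

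Finally, efficacy is exploratory, the only hypothesis concerns safety and tolerability, and the observed-case rule is prespecified and consistent between the documents. N1 and the matched baseline are already reported at each visit, and disposition is summarised. All of this holds and limits the weight of the point. Under moderate dependence the simulated bias is no larger than the standard error. But exploratory status does not turn a mean over patients still being counted into an mITT mean.

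**Conclusion.** The point holds for the Week 12 lesion-count change only. Under Tables 5-2 and 6-2 that row excludes up to about 15% of mITT at the planned attrition. It overstates the mITT reduction if leavers respond worse: at r = 0.5, by about 8%, 5.5% or 3% for 15%, 10.5% or 5.6% missing. The overstatement reaches 10% at m = 15% only if r is about 0.39 or lower, since (1/1.1 − 0.85)/0.15 = 0.394. It is zero if dropout is unrelated to response.

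These sizes rest on an assumed r and on every completer having a Week 12 count. No test or error rate is affected. A reader might infer that a modelled estimate with a confidence interval should become the headline result. The documents do not support that: SAP 5.1.1.3 rules out inferential statistics, and no efficacy timepoint is designated as primary. The change is a worthwhile, inexpensive improvement and does not correct an invalid analysis.

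**What to change.** 1. Reconcile the last timepoint in SAP Table 5-10 with the Day 71 start in Table 6-2, by stating which row takes early-exit counts.
2. Label the observed-case Week 12 rows, for change and percent change, as patients with a Week 12 count, and print N1 beside the mITT N.
3. Add to Table 5-10, for each of the three lesion-count types, one supportive likelihood-based repeated-measures mean change by visit in mITT. Use all observed post-baseline counts, with terms for visit, baseline count and baseline-by-visit, and an unstructured covariance. Report it descriptively, without a p-value or confidence interval, in keeping with SAP 5.1.1.3. The observed-case rows stay.

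The cost is a few lines of SAP text, one standard model and one extra row per lesion type. No new data or patients are needed, and no values are imputed, so it fits Protocol 7.1 and SAP 5.1.1.1.4. The downside is that the added mean relies on missing-at-random: it estimates Week 12 as if leavers had continued like patients with similar earlier counts. The reported reduction may also be slightly smaller.
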